## Informed Consent

Prior to any data collection, participants will provide written (in person) or electronic informed consent via a HIPPA-compliant and secured REDCap electronic form (eConsenting) for participation in the study and data collection procedures, including release of medical records regarding cancer diagnosis and cancer treatment. Research staff will review the study in detail and outline participant involvement during the screening process in person or remotely (via telephone or video conferencing). Research staff will discuss the consent process with the potential participant prior to providing consent. All items in the informed consent will be discussed, including why the study is being conducted, the number of people participating, what is involved in the study, how long the participant will be in the study, the risks and benefits of the study, alternatives to participation,

confidentiality, rights as a participant, and who to call with questions or concerns. Participants will be encouraged to contact research staff any time they have concerns or questions about the study. Each consent is implemented in person or in REDCap. Once an individual agrees to participate and consent electronically, they will electronically sign the informed consent, then hit submit, and a PDF of the completed consent can be automatically generated and saved to preserve the exact consent text along with the research participant's responses. To make this less burdensome, we will collect patients' doctor/medical institution information as part of the medical release form and our staff can directly contact their doctors to confirm agreement and appropriateness of their participation in the study. This approach will not apply to caregivers or providers involved in this study.

## Data Collection

Eligible participants will undergo in person or remote assessments that will include in person, over the phone, video conferencing, and/or web-based data collection.

Data collection will include completion of a written or electronic eConsent form via a secure HIPPA-compliant REDCap survey and the following assessments: (1) Questionnaires assessing demographics, medical history, clinical characteristics (pre- and post-intervention); (2) *Feasibility* will be assessed by rates of accrual to the study; (3) *Acceptability* will be assessed using two Likert-type scales to assess satisfaction (1 = not at all satisfied, 10 = very satisfied) and likelihood to recommend the game to someone else (1 = not at all likely, 5 = very likely) (post-intervention); (4) *Usability* will be assessed with the System Usability Scale (SUS) (post-intervention only), which is a 10-item scale, scored on a 5-point Likert scale (1 = strongly disagree, 5 = strongly agree) (post-intervention); (5) *sources of nutrition information utilized* (6-item checklist) (baseline), (6) *behaviors done based on information consumed online* (6-item checklist) (baseline); (7) *trust and information-seeking* (5-item scale scored on a 7-point Likert scale; 1 = strongly disagree, 7 = strongly agree) (baseline and post-intervention); (8) *vulnerability to misinformation* (3-item scale scored on a 7-point Likert scale; 1 = strongly disagree, 7 = strongly agree) (baseline and post-intervention); (9) *healthy skepticism* (6-item scale scored on a 7-point Likert scale; 1 = strongly disagree, 7 = strongly agree) (baseline and post-intervention); (10) *confidence in sharing and motivation to share information with a medical professional* (2 items from the "Confidence Sharing Information with a Medical Professional" scale scored on a 7-point Likert scale; 1 = not at all confident; 7 = very confident and 2 adapted items to measure degree of motivation; 1 = not at all motivated, 7 = very motivated) (baseline and post-intervention); (11) *Awareness of misinformation* (baseline and post-intervention), (12) *Concern about misinformation and confidence in identifying misinformation* (baseline and post-intervention), (13) *Cancer nutrition information beliefs* (baseline and post-intervention), and (14) brief semi-structured feedback exit interview (post-intervention only).

## 7.0 PARTICIPANT EVALUATION

### 7.1 Study Questionnaires and Assessments

- **Background information**
  - *Demographic and disease characteristics* will include age, gender, race/ethnicity, education level, marital and parental status, income, cancer type, date of diagnosis, and cancer stage.
  - *Behaviors done based on information consumed online* will be assessed with a 6-item checklist asking which behaviors participants have done because of something they saw on the Internet (e.g., "Taken an over-the-counter medicine or supplements, for example, vitamins, minerals, or nutritional supplements").
- **Aim 1:**
  - *Feasibility* will be assessed by rates of accrual and completion of game sessions.
  - *Acceptability* will be assessed using two Likert-type scales to assess satisfaction (1 = not at all satisfied, 10 = very satisfied) and likelihood to recommend the game to someone else (1 = not at all likely, 5 = very likely).
  - *Usability* will be assessed using the System Usability Scale (SUS). The SUS is a reliable, 10-item measure 10-item scale, scored on a 5-point Likert scale (1=strongly disagree; 5=strongly agree), with previously reported excellent internal reliability (Cronbach's  $\alpha = 0.91$ ).
- **Aim 2:**

- *Types of online information* (e.g., *sources of nutrition information utilized*) will be assessed using a 6-item checklist that asks which resources participants or their family members have used to find nutrition information in the past 3 months (i.e., a self-care/health and wellness book, a telephone advice service, a booklet/flyer shared by a health professional, Internet forums, Internet search, social media).
- *Concern about misinformation and confidence in identifying misinformation* will be measured using our 4-item scale in which patients indicate degree to which they agree with statements (e.g., “I feel more confident in my ability to identify misinformation”; 1= strongly disagree, 5 = strongly agree).
- *Cancer nutrition information beliefs* will be measured using a 15-item checklist of common cancer nutrition misinformation and credible nutrition advice. Participants rate the items on a 5-point Likert-scale (1= definitely false, 5 = definitely true).
- **Exploratory outcomes:**
  - *Trust and information-seeking* will be assessed using a validated 5-item measure asking the degree to which individuals trust health information sources (e.g., “I trust the health information I get from my doctor”). This scale is rated on a 7-point Likert scale indicating the degree to which individuals agree with each statement (1 = strongly disagree, 7 = strongly agree).
  - *Vulnerability to misinformation* will be assessed using a validated 3-item measure that asks participants the degree to which they believe they or those in their social network are vulnerable to misinformation (e.g., “I am able to identify news or information that misrepresent reality or is even false.” Items are rated on a 7-point Likert scale (1 = strongly disagree, 7 = strongly agree).
  - *Healthy skepticism* will be assessed using an adapted version of a validated 6-item measure that measures the degree to which participants are skeptical of online posts (e.g., “I am confident in my assessment of this post as emotionally manipulative/overgeneralizes/doesn’t refer to authoritative evidence/cherry picks data”). Items are rated on a 7-point Likert scale (1 = strongly disagree, 7 = strongly agree).
  - *Confidence in sharing information with a medical professional* will be assessed using three adapted items from the validated “Confidence Sharing Information with a Medical Professional” scale. Items ask participants the degree to which they are confident or motivated in sharing information with their doctor (e.g., “How confident are you in your ability to ask a doctor for more information if you don’t understand what he or she said?”). Items are rated on a 7-point Likert scale (1 = not at all confident, 7 = very confident).
  - *Awareness of misinformation* will be measured using our 5-item scale used in our prior study to assess the degree to which the intervention makes users more aware of misinformation types and common tactics (e.g., emotionally charged language, false data; 1 = not at all aware, 7 = fully aware).
- **Exit/debrief questions and interview:**
  - *Game enjoyment/recommendation to others* will be measured using an adapted version of a 12-item scale designed to assess how much individuals enjoyed the game and would recommend it to others (e.g., “I felt content”). Items are rated on a 5-point Likert scale (0 = not at all, 4 = extremely).
  - Using a *semi-structured feedback debrief interview*, participants will be asked about their experiences with the games to inform future iterations and refinement of the escape room game.

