## PROTOCOL SYNOPSIS

Protocol Title	Escape Room: A gamified approach to learning about cancer nutrition information
Protocol Number	
Protocol Sponsor	Fred Hutchinson Cancer Center
Trial Phase	Early Phase/Phase 1
Trial Type	Single arm, open trial
	Aim 1 To evaluate the feasibility, acceptability, and usability of the escape room game intervention among breast cancer patients in active treatment.
Study Objectives	Exploratory Aim 2 To test preliminary efficacy of the escape room game intervention for increasing awareness about types of online misinformation, concern about misinformation, and confidence in the ability to identify misinformation as well as decreasing cancer nutrition misinformation beliefs.
Study Design	Feasibility study (Aims 1 and 2)
Population	Patients with a current diagnosis of breast cancer (Stages I-III) and in active treatment for breast cancer.
Primary Endpoints	Study design and intervention feasibility, acceptability, usability, and potential efficacy of an escape room game will be measured by assessing accrual rate, satisfaction, and usability of the escape room game.
Secondary Endpoints	Awareness and concern about cancer nutrition misinformation and beliefs about cancer nutrition.
Type of Control	N/A (single arm, open trial)
Treatment Group	Escape room game
Treatment Schedule	Intervention (Escape Room Game): 
 
- Pre-game baseline survey
 
- Play the misinformation escape room game intervention in groups of approximately 5 and completed debrief exit interview
 
- Post-game survey
 

Number of participants	N=40 (n=5 breast cancer patients per group)
Estimated duration of study (per participant)	4 weeks
Duration of participation (per participant)	90 minutes

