**Exploratory Aim 2**

To test preliminary efficacy of the escape room game intervention for increasing awareness about types of online misinformation, concern about misinformation, and confidence in the ability to identify misinformation as well as decreasing cancer nutrition misinformation beliefs.

**Hypothesis 2:** Cancer patients will report increases in awareness about types of online misinformation, concern about misinformation, and confidence in the ability to identify misinformation and reductions in believing cancer nutrition misinformation from pre- to post-intervention.

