**3.4 Study Design****Intervention Description**

[figure not shown]
The intervention is an escape room game designed to teach participants how to discern whether cancer nutrition information is accurate or may potentially be misinformation. The content of the game focuses on common tactics used to spread misinformation such as cherry-picking study data, using questionable “expert” influencers, overgeneralization, and misleading headlines. The game is designed to be played in groups of approximately 5, in which players work together to solve a series of puzzles that teaches them about the potential risks of misinformation online. In the present study, the intervention will follow a fictional company (“ZenFusion Wellness”) that is trying to sell its nutritional product (The “Evergreen Diet”) in order to make profits. Throughout the game, players are immersed in the narrative while solving puzzles to learn key themes such as the need to talk to their doctors and look for scientific studies and FDA approvals as well as avoid fads and trends, miracle cures, anecdotal evidence, and targeted and clickbait ads. For example, in one puzzle, participants are asked to “decode” the sensationalist ad headlines and use the codebook to find a password. The headlines are designed to mimic programmatic ads often seen at the bottom of websites with text such as “This one simple trick will help you heal naturally” and “This woman conquered breast cancer through diet alone.” **Figure 1** provides a screenshot of the puzzle. Below, we also outline all five puzzles included in the game.

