- **Puzzle 5:** This puzzle is a maze and represents individual patient health journeys and how to navigate through uncertainty. Each player solves their own maze by clicking on tiles that will form the correct path associated with images that correspond to parts of the care journey that should be adopted (e.g., scientific studies, consultations with medical professionals) rather than those that should be avoided (e.g., fads and trends, miracle cures). Once all players solve their maze, the secret password is revealed.
- **Final Task:** Before the game ends, players are asked to select an option to finish the story. All options are acceptable and lead to winning the game. Players’ discussion of options will preface the next stage of the intervention, which is the hosted debrief.

The game is designed to be played only once by players. It is a collaborative group appropriate for 3-5 players to play together. The length of the game is approximately 30-45 minutes depending on how quickly participants solve the puzzles. The game will be played online via a video-calling platform (i.e. Zoom).

At the end of the game, players are expected to be more aware of possible nutrition misinformation that may be online and to be wiser consumers of online information.

Eight groups of approximately 5 participants (n=40 total) will be recruited and grouped together. Participants will be provided a baseline survey prior to their attendance at the session. Participants will play the misinformation escape room game together with the group and take part in a debrief with a member of the research team immediately after completing the game. Finally, participants will be provided with a post-game survey to complete after the game and debrief session.

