**Table 1. Survey measures to be collected**

	Screening	Baseline	Post -completion of intervention (+ 1 week)
Demographics & clinical characteristics	X	X	
Disease status and treatment		X	X
Behaviors done based on information consumed online (a 6-item background checklist such as "taken over-the-counter medicine")		X	
Aim 1			
Feasibility			X
Acceptability			X
Usability			X
Aim 2			
Types of online information (as measured by 6-item checklist about sources of nutrition information utilized)		X	
Concern about misinformation and confidence in identifying misinformation			X
Cancer nutrition misinformation beliefs (as measured by cancer nutrition beliefs)		X	X
Additional exploratory variables			
Trust and information-seeking		X	X
Vulnerability to misinformation		X	X
Healthy skepticism		X	X
Confidence in and motivation to share information with a medical professional		X	X
Awareness of misinformation		X	X
Exit/debrief questions and interview			
Game enjoyment/recommendation to others			X
Qualitative exit interview			X

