### 13.2 Analyses

Feasibility, acceptability, and usability will be examined by conducting frequency and descriptive statistics for Likert-scale questions and SUS scale. We will conduct preliminary pre/post analyses using repeated measures analysis of variance (ANOVAs) on the misinformation belief scales to assess changes in these beliefs. Finally, we will conduct qualitative analyses on the open-ended questions using a responsive interviewing model for data coding and analysis in which data units or “blocks of information that are examined together” (p. 202) are combined based on the theme they represent. Trained raters will independently review the transcripts and identify passages that include information on participants’ suggestions for modifications to the escape room game. The themes identified in this analysis will inform additional revisions to the intervention as determined by the study investigators.

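### The belief checklist includes credible nutrition advice, but no analysis uses those items, so a fall in misinformation belief could not be told apart from general disbelief

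*Combined protocol and SAP*

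**What the plan says.** Section 7.1 (Aim 2) says that cancer nutrition beliefs "will be measured using a 15-item checklist of common cancer nutrition misinformation and credible nutrition advice". Every item is rated from 1 (definitely false) to 5 (definitely true), so the favourable answer is low for one item type and high for the other. Table 1 and the Data Collection text in Section 6.3 both place the measure at baseline and post-intervention.

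The belief part of Hypothesis 2 (Section 3.2) predicts "reductions in believing cancer nutrition misinformation from pre- to post-intervention". It says nothing about belief in credible advice. Section 13.2 plans repeated measures ANOVAs "on the misinformation belief scales to assess changes in these beliefs" and does not define those scales.

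The labels vary. The synopsis gives the secondary endpoints as "Awareness and concern about cancer nutrition misinformation and beliefs about cancer nutrition", Table 1 has "Cancer nutrition misinformation beliefs (as measured by cancer nutrition beliefs", and Data Collection has "Cancer nutrition information beliefs". No section states which items are misinformation, how many there are, or how a score is formed.

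Section 3.4 describes the game as "designed to teach participants how to discern whether cancer nutrition information is accurate or may potentially be misinformation".

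**The concern.** Discernment has two sides: rejecting false claims and continuing to accept sound ones. The instrument covers both, but the planned analysis names only the first. A player who leaves the session doubting all nutrition statements would lower the misinformation score as much as one who learned to separate good advice from bad.

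The study has a single arm (Section 13.1), so no comparator can show a general shift in responding. The credible items are the only measure of belief in specific nutrition advice. The trust, skepticism and awareness scales in Section 7.1 measure other things.

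What is at stake is how the preliminary belief result can be read when it supports the planned application for a randomised trial (Section 3.1).

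**Working it through.** The documents give no score, SD, effect size, alpha or power for this outcome, so there is no figure of the plan's own to reproduce.

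**Inputs from the documents.** 15 items of two types (Section 7.1); 40 participants in eight groups of about 5 (Sections 3.4 and 6.2).

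**Assumed inputs.** k misinformation items, with k from 5 to 10; shifts of 0.5 Likert points. Let dm be the change on misinformation items and dc the change on credible items.

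**Step 1: formulas.**
- Misinformation-only mean: dm
- Unkeyed mean of all 15 items: (k·dm + (15 − k)·dc)/15
- Difference of means, credible minus misinformation: dc − dm

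**Step 2: three patterns, each with dm = −0.5.**

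| Pattern | dc | Misinformation only | Unkeyed mean, k=5 | Unkeyed mean, k=10 | Difference |
|---|---|---|---|---|---|
| General disbelief | −0.5 | −0.5 | −0.50 | −0.50 | 0 |
| Learning, credible belief unchanged | 0 | −0.5 | −0.17 | −0.33 | +0.5 |
| Learning, credible belief rises | +0.5 | −0.5 | +0.17 | −0.17 | +1.0 |

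Example for the second row at k=5: (5 × −0.5 + 10 × 0)/15 = −0.17. For the third row at k=5: (−2.5 + 5.0)/15 = +0.17.

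The misinformation-only column does not contain dc. Its inability to separate the patterns therefore holds for any shift and any split, not just for these assumed values.

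The unkeyed mean falls most under general disbelief. When credible belief rises it can be close to zero: (−3.5 + 4.0)/15 = +0.03 at k=7 and (−4.0 + 3.5)/15 = −0.03 at k=8. A fall in credible belief would count as success, and a rise could cancel a real gain.

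**Step 3: why a difference of two means and not one keyed total.** With misinformation items reversed, general disbelief moves a 15-item total by (2k − 15) × 0.5/15. That is −0.17 at k=5 and +0.17 at k=10, and it is never zero because 15 is odd. The difference of means gives 0 under uniform disbelief at every split.

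**Step 4: precision of the difference.** Assume equal SDs of change on the two means, a correlation r between the two changes of 0.3 to −0.3, and a within-group ICC of 0.10.
- Design effect: 1 + (5 − 1) × 0.10 = 1.4
- t on 7 df (eight groups): 2.365
- Half-width for one mean at SD 1.0: 2.365 × 1.0 × √1.4/√40 = 0.44
- SD factor for the difference: √(2(1 − r)) = 1.18 at r = 0.3 and 1.61 at r = −0.3
- Half-width for the difference: 0.52 to 0.71 at SD 1.0, and 0.26 to 0.36 at SD 0.5

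So a discernment gain of 0.5 would exclude zero at SD 0.5 but not at SD 1.0. A gain of 0.25, as when credible belief falls by half as much as misinformation belief, would not exclude zero in any of these clustered settings.

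**The case against.** The strongest reply is that the plan already measures what it sets out to measure. Hypothesis 2 and Section 13.2 both point to misinformation belief, and Hypothesis 2 gives its direction. Sections 2.1 and 3.1 state the goal as reducing vulnerability to believing misinformation, and no section plans a claim of improved discernment. The game also steers players towards sound sources: Puzzle 5 rewards "parts of the care journey that should be adopted", such as scientific studies and medical consultations, and a nutrition expert leads the debrief (Section 7.2). Aim 2 is exploratory, and a single arm cannot attribute change to the game under any scoring.

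All of this stands, and it makes the point minor. It does not give the credible items an analysis, and it does not let a misinformation-only score show the skill that Section 3.4 says the game teaches.

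A reader might go further in two ways that the documents do not support.
- One is that most plausible scorings fail. Any such count depends on which scorings are listed. Separate means for the two item types also fit the text, and the plural in Section 13.2 is compatible with them. The unkeyed mean is the weakest reading, since it would count belief in credible advice as misinformation belief.
- The other is that Section 2.2 recognises general disbelief as a harm, because it mentions patients avoiding beneficial behaviours. That sentence describes a consequence of misinformation, not of disbelief in general.

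**Conclusion.** The concern holds as a minor point, worth considering. The plan collects ratings of credible advice at both times and states no analysis of them. The misinformation-only score is a valid test of Hypothesis 2 as written, but it cannot distinguish discernment from general disbelief, whatever the effect size or item split. That conclusion rests on no assumed number.

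The illustrated shifts, item splits, SDs, correlations and ICC are all assumptions, and no bias in this trial has been sized. A reader might infer that Hypothesis 2 cannot be tested, or that the game is likely to produce blanket disbelief. The documents support neither. No Aim 1 hypothesis is affected.

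**What to change.** In Section 7.1, state which of the 15 items are misinformation and which are credible advice, and score each set as a separate mean. Use one label for the measure throughout.

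In Section 13.2, keep the misinformation mean as the Hypothesis 2 belief outcome. Add, as supporting exploratory results, the pre/post change with 95% CI for the credible mean and for the difference (credible minus misinformation), with intervals that allow for game group. Any statement about discernment should rest on the difference, shown beside the credible-advice change. No pass/fail rule is needed.

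The cost is wording and two extra exploratory estimates. All 15 items are already collected at both times, so there is no added burden or sample, and nothing is lost if the scoring is fixed before analysis. The drawback is that the difference may be noisier than either mean, with an SD of change 1.18 to 1.61 times as large under the assumptions above. It should be reported as an estimate with its interval.
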